## **Background**

Osteoporosis is most commonly treated with anti-resorptive therapy. The two most widely used anti-resorptive agents are bisphosphonates (either alendronate or zoledronic acid) and denosumab. Bisphosphonates adhere to the bone and when taken up by the osteoclasts, bisphosphonates interfere with their cytoskeleton and the osteoclasts become unable to resorb bone and may undergo apoptosis [1]. Denosumab is an antibody against receptor-activator of nuclear factor kappa-B ligand (RANKL) that prevents recruitment and differentiation of mature osteoclasts [2]. Both agents markedly decrease bone resorption and fracture risk [3-5]. First line treatment is alendronate that by far is the cheapest. In Denmark denosumab can only be reimbursed if the patient cannot take alendronate due to side effects, treatment failure or contra indications why denosumab is second line therapy. Zoledronic acid is administered intravenously and therefore in clinical practice almost exclusively administered in hospitals, which limits its use.

It has become evident that long-term anti-resorptive therapy (bisphosphonates and denosumab) may lead to serious side effects such as atypical femoral fractures [6] or osteonecrosis of the jaw [7]. This has obviated the need for an evidence-based assessment of the balance between long-term benefits and risks. The adhesion of bisphosphonates to bone is very strong meaning that the biological half-life is years and that the effect on bone remains long after administration [8]. In accordance with this the alendronate extension study showed that despite stopping treatment after five years the anti-fracture efficacy regarding non-vertebral and radiological vertebral fractures persists for an additional five years in patients with BMD T-score > -2.5 at the femoral neck, no fractures during treatment, and no previous vertebral fracture [9-10]. Zoledronic acid adheres even stronger to bone than alendronate and is administered intravenously once yearly. Zoledronic acid treatment can be discontinued after three years based on the same criteria as alendronate [11].

Compared to bisphosphonates the pharmacokinetics of denosumab is completely different. Denosumab is cleared within six months and does not adhere to bone meaning that after discontinuation of denosumab bone resorption increases again. In addition, the bone mass gained during two years of therapy is completely lost within one year after discontinuation [12], and recent evidence even suggests that discontinuation of long-term therapy may lead to hypercalcemia [13] and multiple vertebral fractures [14-17] due to increased bone-turnover. At present denosumab treatment is considered to be life-long.

## **Aims**

To investigate if infusion of zoledronic acid can prevent increases in bone turnover and bone loss in patients previously treated with denosumab and if there is difference between infusing zoledronic acid at six or nine months after the last injection of denosumab or when bone turnover is increased. The reason for investigating different time points for the infusion of zoledronic acid is that if bone remodelling is strongly suppressed by the previous denosumab treatment, bisphosphonate may not adhere well enough to the bone surface to inhibit resorption once the effect of denosumab wears off. It has been demonstrated that some patients still have completely suppressed markers of bone turnover six months after the last injection but also that most patients have regained some resorptive activity three months later [12].

## **Study population and methods**

### **Design**

A randomized open label, interventional study in 60 patients investigating if treatment with zoledronic acid prevents bone loss after denosumab treatment when administrated six (6-month group, n=20) or nine months (n=20, 9-month

group) after last injection of denosumab or when bone turnover is increased (n=20, observation group). Forty patients will be allocated to the two intervention groups and 20 patients will be followed without treatment for up to 12 months after the last denosumab treatment. The patients in the observation group and the nine months group will be monitored monthly and if p-carboxy-terminal collagen crosslinks (p-CTX) increases above 1.26µg/l (50% above the normal range for postmenopausal women and elderly men) infusion of zoledronic acid will be administered. Furthermore, a DXA scan (lumbar spine and hip sites) will be performed after three months in the observation group. If BMD has decreased more than 5% at the lumbar spine or total hip, infusion of zoledronic acid will be administered. Finally, if a patient in the 9 months group or the in the observation group suffers an osteoporotic clinical vertebral or hip fracture, infusion of zoledronic acid will be administered.

The patients will be given a single infusion of zoledronic acid as the increase in bone turnover seen after stopping denosumab seems most prominent in the first year [12]. The patients will be monitored with DXA 6, 12 and 24 months after the infusion of zoledronic acid. Zoledronic acid will be re-administered if BMD has decreased more than 5% at the lumbar spine, total hip or femoral neck.

If p-CTX increases above 1.26 µg/l during the 2nd year a second infusion of zoledronic acid will be administered.

#### **Co-primary endpoint**

- Change in lumbar spine BMD from baseline to 6 months after the zoledronic acid infusion.
- The proportion of patients who fails to maintain BMD (total hip, femoral neck and spine). Failure is defined as  $\geq 3$  % BMD loss at the lumbar spine or  $\geq 5$  % BMD loss at the femoral neck or total hip.

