#### **Secondary endpoints**

- Changes in total hip, femoral neck and lumbar spine BMD from baseline to one year after the zoledronic acid infusion.
- Changes in total hip, femoral neck and lumbar spine BMD from baseline to two years after the zoledronic acid infusion.
- Changes in trabecular bone volume fraction (bone volume/tissue volume, BV/TV) and cortical porosity measured by high-resolution peripheral quantitative computed tomography (HR-pQCT) scan at the radius and tibia from baseline to one year after the zoledronic acid infusion.
- Changes in p-CTX and p-procollagen type I N-terminal propeptide (p-PINP) from baseline to six months after the zoledronic acid infusion.
- Changes in p-CTX and p-PINP from baseline to 12 months after the zoledronic acid infusion.
- Morphometric vertebral fractures assessed by vertebral fracture assessment (VFA) one and two years after the zoledronic acid infusion.

---

 Electrochemiluminescence immunoassay (ECLIA) will be used.

 Reference range: Women 30-50 years: 0,04 - 0,59 µg/l. Women > 50 years: 0.03-0.83 µg/l. Men 30-50 years: 0,09 - 0,63 µg/l. Men 50-70 years: 0.04-0.84 µg/l. Men > 70 years: 0,08 – 1,05 µg/l.

 ECLIA will be used.

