**Duration of study**

Included patients will be part of the study for up to 30 months. The primary endpoints will be investigated 12 months after infusion of zoledronic acid. The participants will receive a letter from the investigator after the termination of the study with information about the study results.

Study plan

Group 1: 6-month group	Baseline	M1	M3	M6	M12	M16	M20	M24
Informed consent	X							
Medical history	X							
Physical examination	X							
Bone markers	X	X	X	X	X	X	X	X
Biochemistry	X				X			
HR-pQCT	X				X			
DXA	X			X	X			X
Zoledronic acid treatment	X							
Fracture history	X				X			X
Telephone call						X	X	

Group 2: 9-month group	Baseline	M1+2 	M3	M4	M6	M9	M15	M19	M23	M27
Informed consent	X									
Medical history	X									
Physical examination	X									
Bone markers	X	X	X	X	X	X	X	X	X	X
Biochemistry	X						X			
HR-pQCT	X						X			
DXA	X		X			X	X			X
Zoledronic acid treatment			X							
Fracture history	X						X			X
Telephone call								X	X	

Group 3: Observation group	Baseline	M1-5 	M3	Mx 	Mx+1	Mx+2	Mx+6	Mx+12	Mx+16	Mx+20	Mx+24
Informed consent	X										
Medical history	X										
Physical examination	X										
Bone markers	X	X		X	X	X	X	X	X	X	X
Biochemistry	X							X			
HR-pQCT	X							X			
DXA	X		X	X			X	X			X
Zoledronic acid treatment				X							

Fracture history	X							X			X
Telephone call									X	X	

 M1 + M2: Month 1 and month 2 after baseline.

 M1 - M5: Month 1 to month 5 after baseline.

 Mx: months after baseline, depends on when the specified levels of p-CTX or BMD loss are achieved

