### **Statistical analysis and power calculation**

Baseline characteristics of the three groups will be presented using descriptive analysis and compared using ANOVA and post-hoc unpaired t-tests if ANOVA demonstrates differences between the groups. Changes in bone mineral density one year after the zoledronic acid infusion within groups will be investigated using paired-sample t-tests and compared with the changes reported after stopping denosumab after two years [12] for the three groups combined and individually using one-sample t-test. The proportion of patients who fails to maintain BMD will be compared between groups using chi-sq test. Changes in bone mineral density, HRpQCT measures and markers of bone turnover will be compared between groups using mixed model analysis. Exploratory analyses will include multiple regression analyses aiming at identifying baseline factors or changes occurring at three or six months, which affect the change in BMD one year after the zoledronic acid infusion. Factors included in this analysis will be gender, age, years of treatment with denosumab, baseline BMD, baseline bone turnover markers, change in bone turnover markers three and six months after the zoledronic acid infusion.

Based on a previous study a 5% decrease in lumbar spine BMD can be expected during the first year after discontinuation with a 3% standard deviation [12]. The hypothesis is that treatment with zoledronic acid can decrease this bone loss. Eighteen patients will be needed to demonstrate a bone loss  $\geq 2.5$  % using a paired-sample t-test with a power of 90% and level of significance of 5%. If the decrease is less than that BMD is maintained and the hypothesis can be accepted. To account for dropouts n is increased to 20 in each group. As comparisons between the different treatment regiments suggested in this protocol never have been done before, we cannot estimate differences between groups. However, the least significant change in lumbar spine BMD using DXA is 3%. The SD of lumbar spine BMD in our facility is 3% [18]. To be able to demonstrate a difference in change in lumbar spine BMD between the three groups equal to the least significant change using independent samples t-test we need 16 patients in each group with a standard

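### The lumbar spine co-primary is set at 6 months after infusion in one section and at 12 months in another, and the failure co-primary names no visit of its own

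*Combined protocol and SAP*

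**What the plan says.** - **Co-primary endpoint.** The first co-primary is "Change in lumbar spine BMD from baseline to 6 months after the zoledronic acid infusion". The second is the proportion of patients who fail to maintain BMD. It has loss thresholds for the spine and hip sites but no time point.
- **Secondary endpoints.** The list includes "Changes in total hip, femoral neck and lumbar spine BMD from baseline to one year after the zoledronic acid infusion".
- **Duration of study.** "The primary endpoints will be investigated 12 months after infusion of zoledronic acid". The noun is plural, so the sentence appears to cover both co-primaries.
- **Statistical analysis and power calculation, within groups.** "Changes in bone mineral density one year after the zoledronic acid infusion within groups will be investigated using paired-sample t-tests". The same sentence compares these changes with a published untreated series by one-sample t-test. The exploratory regression looks for factors "which affect the change in BMD one year after the zoledronic acid infusion".
- **Same section, between groups.** "The proportion of patients who fails to maintain BMD will be compared between groups using chi-sq test". A mixed model compares BMD changes between groups. Neither sentence names a visit.
- **Same section, success criterion.** After powering for a 2.5% loss, the plan says "If the decrease is less than that BMD is maintained and the hypothesis can be accepted". No post-infusion visit is given.
- **Design and the study plan tables.** DXA is scheduled at 6, 12 and 24 months after infusion in every group.

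**The concern.** A primary endpoint needs one visit. Here the lumbar spine change at one year is secondary according to the endpoint list and primary according to the duration section. The 6-month change is primary according to the endpoint list, yet no analysis sentence names it. The failure endpoint takes its only visit from the sentence that contradicts the endpoint list.

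The answer to whether bone mass was maintained may depend on the visit. The two visits are six months apart in a period when the effect of denosumab is wearing off, so they estimate different quantities. If the text stays as it is, the visit that decides the trial, and the test that goes with it, remain to be chosen at analysis.

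**Working it through.** **1. The plan's own sample size.** Inputs, all from the statistical section: loss 2.5%, SD 3%, power 90%, significance 5%. The standardised effect is 2.5/3 = 0.833. A two-sided paired t-test (noncentral t) needs n = 17.2, so 18, as stated. Power is 91.5% at 18 and 94.2% at 20. For the between-group figure, 2 × (1.960 + 0.842)² × (3/3)² = 15.7, so 16 per group, as stated (exact t gives 16.7, so 17). The arithmetic reproduces, but no post-infusion visit enters it, so it does not show which visit was powered.

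**2. The visit attached to each element.**

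| Element | Section | Visit after infusion |
|---|---|---|
| Lumbar spine co-primary | Co-primary endpoint | 6 months |
| Primary endpoints (plural) | Duration of study | 12 months |
| Lumbar spine change, secondary | Secondary endpoints | one year (also two years) |
| Failure co-primary, definition | Co-primary endpoint | none |
| Failure co-primary, chi-square | Statistical analysis | none |
| Paired and historical t-tests | Statistical analysis | one year |
| Mixed model between groups | Statistical analysis | none |
| 2.5% criterion | Statistical analysis | none |

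**3. What the two readings mean in time.** Nominal infusion is at study month 0, 3 and no later than 6 (Treatment, under Investigations). This is 6, 9 and up to 12 months after the last denosumab injection. Add 6 or 12.

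| Group | From last injection | From study baseline |
|---|---|---|
| 6-month | 12 versus 18 | 6 versus 12 |
| 9-month | 15 versus 21 | 9 versus 15 |
| Observation | up to 18 versus 24 | up to 12 versus 18 |

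**4. Does the planning loss choose a visit?** The plan expects a 5% loss in the first year after discontinuation. In the 6-month group, month 12 counted from the last injection is the 6-month post-infusion scan; counted from study baseline it is the 12-month scan. In the 9-month group neither visit falls at month 12 on either clock. The figure therefore does not settle the question.

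**5. Does the scan schedule choose a visit?** The 6- and 12-month post-infusion scans are M6 and M12, M9 and M15, and Mx+6 and Mx+12. Both visits exist in every group, so the schedule fits either reading.

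**6. Scans available to a failure rule, up to 12 months after infusion.**

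| Group | All scans after baseline | Of these, after infusion |
|---|---|---|
| 6-month | 2 (M6, M12) | 2 |
| 9-month | 3 (M3, M9, M15) | 2 |
| Observation | up to 4 (M3, Mx, Mx+6, Mx+12) | 2 |

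The groups differ only in scans taken before or at infusion.

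**7. Illustration of an open choice.** Suppose one endpoint were tested at two-sided 5% at both visits and a positive result at either were claimed. The false-positive rate would be 1 − 0.95² = 9.75% if the visits were independent, 9.1% at correlation 0.5 and 7.0% at 0.9. The correlations are assumed, and the plan does not propose such a rule.

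**The case against.** The strongest reply is that the endpoint section governs. On that view the lumbar spine co-primary is at 6 months, the mixed model compares the groups there, and the one-year paired and historical tests serve the one-year secondary endpoint. Part of this stands: the mixed model can include the 6-month scan, so it would be wrong to say that a 6-month co-primary has no analysis. But no rule of precedence is stated, and the study is powered on a paired within-group test, which is described only at one year.

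For the failure endpoint, it can be said that the documents do not conflict: two places are silent and one gives 12 months. That is correct, and 12 months is the only visit the documents offer. It comes, however, from a sentence that cannot be right for both co-primaries as they are now defined.

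Four stronger readings are tempting, and the documents do not support them:

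- **Failure is counted at any scan, so the groups have unequal chances to fail.** No section states such a rule, and post-infusion scans are the same in all groups. Percentages for it need an assumed correlation between scans and depend on how the 3% is read. At correlation 0.5, false spine failure by 12 months is 4.5%, 6.3% and up to 7.8% if 3% is a two-sided 95% limit for no change. It is 25.5%, 32.2% and up to 37.3% if 3% is the SD of individual changes. These figures are not part of this point.
- **Data were seen before the visit was fixed.** The document is dated January 2018 and recruitment was planned from November 2016, so some scans could have existed. Nothing says that they were examined, and Research plan and facilities places analysis in May to October 2020.
- **One visit makes success easier.** The documents give no untreated loss at 6 months, so this cannot be judged.
- **Choosing 12 months delays the read-out.** All analysis is planned after the trial ends in April 2020, so neither choice moves it.

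**Conclusion.** The point holds as a contradiction in current text. One co-primary has two visits, and the other has no visit except the one implied by the contradicting sentence. It must be corrected because it concerns the definition of the primary endpoints.

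Its size is a six-month difference in the primary time point in every group, with one-year within-group tests that do not match a 6-month co-primary. The month counts assume infusion on the nominal schedule; patients treated early on the p-CTX, BMD or fracture criteria would shift. No numerical bias is claimed, and the sample size arithmetic is not in question.

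**What to change.** Before analysis, reconcile Co-primary endpoint, Secondary endpoints, Duration of study, and Statistical analysis and power calculation:

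1. Name one post-infusion visit, 6 or 12 months, for each co-primary, and correct the sections that disagree. If 12 months is chosen for the lumbar spine, move the 6-month change to the secondary list.
2. State which test applies at that visit, within and between groups, and that the 2.5% criterion refers to it. Label the one-year paired and historical tests as primary or secondary accordingly.
3. Define failure on post-infusion DXA, on the same schedule in every group. A single named visit is simplest; a cumulative rule over post-infusion scans would also be balanced. Do not count scans taken before or at infusion.

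The cost is wording only. Both scans are already scheduled in all groups, and the planned analysis date does not change. If 6 months is kept, the one-year historical comparison does not match it and must be labelled secondary or given a justified 6-month comparator.

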#### **Secondary endpoints**

- Changes in total hip, femoral neck and lumbar spine BMD from baseline to one year after the zoledronic acid infusion.
- Changes in total hip, femoral neck and lumbar spine BMD from baseline to two years after the zoledronic acid infusion.
- Changes in trabecular bone volume fraction (bone volume/tissue volume, BV/TV) and cortical porosity measured by high-resolution peripheral quantitative computed tomography (HR-pQCT) scan at the radius and tibia from baseline to one year after the zoledronic acid infusion.
- Changes in p-CTX and p-procollagen type I N-terminal propeptide (p-PINP) from baseline to six months after the zoledronic acid infusion.
- Changes in p-CTX and p-PINP from baseline to 12 months after the zoledronic acid infusion.
- Morphometric vertebral fractures assessed by vertebral fracture assessment (VFA) one and two years after the zoledronic acid infusion.

---

 Electrochemiluminescence immunoassay (ECLIA) will be used.

 Reference range: Women 30-50 years: 0,04 - 0,59 µg/l. Women > 50 years: 0.03-0.83 µg/l. Men 30-50 years: 0,09 - 0,63 µg/l. Men 50-70 years: 0.04-0.84 µg/l. Men > 70 years: 0,08 – 1,05 µg/l.

 ECLIA will be used.

### **Study population**

#### Inclusion criteria

- Postmenopausal women (postmenopausal for at least two years)
- Men above 50 years
- Treatment for at least two years with denosumab
- Last denosumab injection less than five months ago

#### Exclusion criteria

- Low-energy vertebral fracture at any time
- Low-energy hip fracture within the last 12 months
- BMD T-score < -2,5 (lumbar spine, total hip or femoral neck)
- Alendronate treatment for more than three years prior to denosumab treatment
- Ongoing treatment with glucocorticoids
- Metabolic bone disease
- Hormone replacement therapy
- Cancer
- Estimated glomerular filtration rate (eGFR) < 35 mL/min
- Allergy to zoledronic acid
- Hypocalcaemia
- Contraindications for zoledronic acid according to the SPC

### **Fertility and pregnancy**

Pregnancy testing and precautions concerning female fertility will not be relevant since the women participating in the study are postmenopausal. There are no special considerations with respect to the male fertility and treatment with zoledronic acid.

### **Randomization**

The patients will be randomized to infusion of zoledronic acid administered either six (6-month-group, n=20) or nine months (9-month group, n=20) after the last denosumab injection or to observation in the form of monthly monitoring of bone resorption (observation group, n=20). If p-CTX increases above 1.26 ug/l in patients in the observation group or the nine months group, zoledronic acid will be administered. If BMD decreases by more than 5% at any site after three months in the observation group, infusion of zoledronic acid will be administered.

The randomization code will be generated by the hospital pharmacy, Aarhus University Hospital. Participants will be randomized in blocks of 6.

---

 In case of dropouts the randomization codes will be reused. The codes will be randomized amongst the new participants.

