*Treatment:* An intravenous infusion of 5 mg zoledronic acid will be administered at study day 0 (6-months group), at month three (9-months group), or depending on increase in p-CTX, decrease in BMD, or the occurrence of an osteoporotic clinical vertebral or hip fracture, but no later than at month 6 (observation group). The patients will be monitored with DXA 6, 12 and 24 months after the infusion of zoledronic acid. Zoledronic acid will be re-administered if BMD has decreased more than 5% at the lumbar spine, total hip or femoral neck. If p-CTX increases above 1.26  $\mu\text{g/l}$  during the 2nd year a second infusion of zoledronic acid will be administered.

*Fracture history:* Participants will be questioned about incident fractures at months 12, 15, or x+12 and again at months 24, 27, or x+24. Information will be confirmed using discharge notes from hospitals.

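### The month-3 BMD trigger for infusion in the observation group is given with two different site lists, which disagree for patients whose only loss above 5% is at the femoral neck

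*Combined protocol and SAP*

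**What the plan says.** Two sections of the combined protocol and SAP state the rule for the month-3 scan.

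- **Randomization:** infusion is given "If BMD decreases by more than 5% at any site after three months in the observation group".
- **Design:** "If BMD has decreased more than 5% at the lumbar spine or total hip, infusion of zoledronic acid will be administered".

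Design describes the scan as follows: "a DXA scan (lumbar spine and hip sites) will be performed after three months in the observation group". It does not restrict the hip measurement to the total hip.

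Elsewhere the femoral neck is its own site. The second co-primary endpoint counts as failure a 5% or greater "BMD loss at the femoral neck or total hip". The T-score exclusion applies at "lumbar spine, total hip or femoral neck". The re-infusion rule, in Design and again under Investigations (Treatment), names the same three sites.

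The remaining references to the trigger name no site. Footnote 3 of the study plan says the infusion month "depends on when the specified levels of p-CTX or BMD loss are achieved". Investigations (Treatment) mentions only a decrease in BMD and sets the outer limit: "but no later than at month 6 (observation group". Safety and ethical considerations refers to a significant decrease in bone mass.

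**The concern.** This rule decides when study drug is given. Safety and ethical considerations also lists the month-3 scan among the measures meant to limit risk in patients left untreated after denosumab. It should therefore have one reading.

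Take an observation patient who has lost more than 5% at the femoral neck and at neither other site, with no p-CTX or fracture trigger. Under Randomization, leaving this patient untreated after the scan departs from the protocol. Under Design, read as a full list, it does not. Staff could handle two such patients differently, and a monitor could not classify either case consistently. The infusion month also fixes the patient's later visits, which are counted from it.

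**Working it through.** The discrepancy is textual. The arithmetic only indicates how many patients it might touch.

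**Step 1: the two rules compared.**

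| Sites with loss above 5% at month 3 | Randomization | Design, as a full list |
|---|---|---|
| Lumbar spine or total hip, with or without femoral neck | Infuse | Infuse |
| Femoral neck only | Infuse | No BMD trigger; month 6 at the latest |
| None | No BMD trigger | No BMD trigger |

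The rules part only in the second row. The longest delay is 6 − 3 = 3 months, and less if p-CTX or a fracture triggers infusion first.

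**Step 2: can another section settle it?** No. Footnote 3, Investigations (Treatment) and Safety and ethical considerations name no site. Within Design, the femoral neck is missing from the month-3 rule but present in the re-infusion rule in the next paragraph, so the omission could be deliberate.

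**Step 3: how many patients?** The documents give the group size (20) and one SD, 3% for lumbar spine BMD (Statistical analysis and power calculation). They give no month-3 means, hip SDs or between-site correlations. The assumptions are:

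- mean change −1%, −2% or −3%, the same at each site;
- SD 3% at the spine, 2.5% at the total hip, and 2.5%, 3%, 3.5% or 4% at the femoral neck;
- correlation 0.4, 0.5 or 0.6 between spine and hip sites, and 0.7 or 0.8 between the two hip sites.

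This makes 3 × 4 × 3 × 2 = 72 settings, each simulated from a trivariate normal distribution with 400,000 draws.

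- P(spine or total hip below −5%) = 0.121 to 0.370.
- P(any of the three below −5%) = 0.140 to 0.475.
- The excess *e*, taken as the difference within each setting, is P(femoral neck only) = 0.018 to 0.108.

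If a share *s* has already been infused on p-CTX, independently of BMD, the affected probability is *q* = (1 − *s*)*e*. The expected number is 20*q*, and the chance of at least one is 1 − (1 − *q*)^20.

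| Share already infused | Expected number of 20 | Chance of at least one |
|---|---|---|
| None (upper bound) | 0.4 to 2.2 | 31% to 90% |
| 25% | 0.3 to 1.6 | 24% to 82% |
| 50% | 0.2 to 1.1 | 17% to 67% |
| 75% | 0.1 to 0.5 | 9% to 42% |

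For example, at the top of the 50% row *q* = 0.5 × 0.108 = 0.054, so 20*q* = 1.08 and 1 − 0.946^20 = 0.67. Holding the femoral neck SD at or below 3% changes the 50% row to 0.2 to 0.8 patients and 17% to 54%.

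**Step 4: is there still time to change the wording?** The document is dated 29 January 2018 and recruitment was planned to end in October 2017 (Research plan and facilities). If the last baseline visit was then, the last month-3 scan falls around January 2018. If October 2017 was the last enrolment, the criterion "Last denosumab injection less than five months ago" together with a baseline six months after that injection puts baseline one to six months later. Those scans would fall in about February to July 2018.

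**The case against.** The strongest reply is that this is an ambiguity, not a contradiction. Design does not say that only the two listed sites count, so infusing the femoral-neck-only patient at month 3 satisfies both sections. The Randomization text is also a condensed restatement: it omits the fracture trigger that Design includes. Its reference to any site could be shorthand for the two sites in Design, and Investigations describes the DXA as covering two regions, spine and hip. This narrows the point without removing it. Waiting satisfies one section and not the other, and the shorthand reading sits badly with a scan of several hip sites and a protocol that repeatedly names the femoral neck separately. If shorthand was meant, Randomization still needs correcting.

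Four further points have weight.

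- Randomization places the trigger after three months but sets no deadline for the infusion. That waiting breaches it is a fair inference, not an express term.
- The counts rest on assumptions and may lean high. The Background links bone loss after stopping denosumab to raised turnover, so patients already infused on p-CTX may be those losing most bone. With half infused and an assumed correlation of 0.3 to 0.7 between p-CTX and bone loss, the figures become 0.04 to 0.95 of 20 and 4% to 62%. With hip means half the spine mean, femoral neck SD 2% to 3% and independent p-CTX, they are 0.02 to 0.42 of 20 and 2% to 35%.
- Monthly p-CTX, the fracture trigger and the month-6 limit still protect these patients.
- The infusion month varies by design in this group, so a shift within the permitted window does not upset the analysis. However, BMD change is measured from baseline, so loss during a delay does count towards the endpoints.

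**Conclusion.** The concern holds and is minor. One treatment trigger is stated with two site lists, and the documents do not say which governs. That conclusion rests on the text alone and is made with high confidence.

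The consequence is limited to isolated femoral neck loss in one arm of 20, with a delay of at most three months. The number affected cannot be estimated from the documents; under the assumptions shown it is probably none to two. By definition these patients have no spine loss above 5% at that scan, so the likely effect on the lumbar spine co-primary endpoint is small. Femoral neck loss does count in the failure co-primary endpoint, but too few patients are involved to alter the planned comparison. Sample size and analyses stand as written.

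**What to change.** State the month-3 trigger in both Design and Randomization as a loss above 5% at the "lumbar spine, total hip or femoral neck", matching the re-infusion rule, and have Investigations (Treatment) refer to it. Footnote 3 of the study plan can stay as it is. If the femoral neck was left out of Design on purpose, say so and narrow the Randomization wording instead.

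For patients already past the month-3 scan, record which rule was applied and report how many had isolated femoral neck loss above 5%. This is the main action, because the wording change may come too late for most patients.

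The cost is one sentence in each of two sections, a cross-reference, and a check of at most 20 scans. Including the femoral neck could bring forward about two infusions among the 20 patients at most, under the assumptions above.
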